## SUMMARY

**Rationale:** To date the majority of surgical interventions is performed in day care and patients are being discharged soon after the first critical postoperative period. At home, patients have limited options to contact the hospital in case of severe pain and nausea. We have provided day care surgical patients with a smartphone application for remote monitoring that is configured to self-record postoperative pain and nausea after being discharged from hospital. Furthermore, it provides a messaging service to contact the hospital in case of (severe) pain or nausea. Despite the promising initial patient experiences of such an application, we do not know whether remote monitoring with a smartphone application improves the patient's experience during the recovery period.

**Objective:** To evaluate the experienced quality of recovery after day care surgery between patients provided with a smartphone application for remote monitoring and patients receiving standard of care (no remote monitoring).

**Study design:** (Non-blinded) randomized controlled trial with mixed methods design

**Study population:** Adult patients (aged 18 years or older) scheduled for day care surgery

**Intervention (if applicable):** The intervention group receives the smartphone application for remote monitoring during weekdays from 8 am to 17 pm up to 7 days after surgery. With this application, patients are able to record experienced pain and nausea. In addition, they can send messages to the hospital. Daily monitoring is performed by an anaesthesia professional who will contact the patient in case severe pain or nausea is reported in the app. The control group receives standard of care (with post-discharge verbal and paper instructions).

**Main study parameters/endpoints:** The main study endpoint is the difference between patients using remote monitoring and patients not using remote monitoring in perceived quality of recovery measured with the QoR-15 questionnaire on the 7th day after day care surgery. Secondary endpoints are 1) the overall score on the Quality of Recovery-15 at day 1, 4 and 7 post discharge, 2) the perceived quality of hospital aftercare and 3) experienced psychological effects of remote monitoring during postoperative recovery from day care surgery.

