**Nature and extent of the burden and risks associated with participation, benefit and group relatedness:** Participating in this study does not pose any additional risks either for patients allocated to the intervention group with remote monitoring or for patients allocated to the standard of care group. Patients in the remote monitoring group are being asked to use a smartphone application to record pain and nausea daily for up to 7 days post discharge. Recording pain and nausea will take 2 minutes daily. Patients from both groups are being asked to fill in the validated QoR-15 questionnaire one day before admission and on the 1st, 4th and 7th day post discharge and this will take 2.5 minutes. No extra hospital visits, physical examinations or tests are required. Patients in the remote monitoring group could benefit

from participating in the study because they are monitored daily by a healthcare professional. Therefore, severe pain, nausea and possibly other complications can be noticed and managed earlier.

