### c. Secondary Objective(s)

To assess the experienced postoperative pain (POP) between patients provided with a smartphone application for remote monitoring and patients receiving standard of care (no remote monitoring) after day care surgery.

To assess the experienced post discharge nausea and vomiting (PDNV) between patients provided with a smartphone application for remote monitoring and patients receiving standard of care (no remote monitoring) after day care surgery.

To assess the difference in the number of surgical complications rated with the Clavien Dindo classification of surgical complication between patients provided with a smartphone application for remote monitoring and patients receiving standard of care (no remote monitoring) after day care surgery.

To assess the difference in the number of re-admissions between patients provided with a smartphone application for remote monitoring and patients receiving standard of care (no remote monitoring) after day care surgery.

To assess the difference in the number of hospital contacts / general practitioner between patients provided with a smartphone application for remote monitoring and patients receiving standard of care (no remote monitoring) after day care surgery.

To assess the difference in experienced quality of communication with the hospital staff between patients provided with a smartphone application for remote monitoring and patients receiving standard of care (no remote monitoring) after day care surgery.

To assess the experienced psychological effects remote monitoring in patients recovering from day care surgery

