non-steroid inflammatory drug (NSAID), metoclopramide, pantoprazole and if they underwent a surgical procedure with intermediate risk for complications, they also receive tramadol or opioids.

In addition to standard care as delineated above, patients in the intervention group (remote monitoring after discharge) will have the monitoring application installed on their personal smartphone. Once they are back home, they can start recording pain and nausea and may ask questions about their recovery within the application. Once a day patients receive a push notification to record pain and nausea. The application is operational up to 7 days post discharge. After this period the application is disconnected from the Thuismeten (Luscii) © server.

In case of recording unbearable pain and nausea or asking a question and being in need for help or assistance, an anaesthesia medical assistant will contact these patients during office hours from 08:00 to 16:30 by using the applications' messaging service or by telephone. First the medical assistant will perform an initial triage of the patients in need, subsequently pain and nausea reports and additional questions that appear as an alert in the electronic back office systems of Thuismeten (Luscii) © will be addressed. The alerts are set to the in-app question 'do you want something to be done about your pain or nausea?' or an increase of 3 points numerical rating scale (NRS) for pain and additional questions asked in the apps messaging service. During triage, the medical assistant will follow a protocolled workflow to assess actions to be taken (APPENDIX II triage workflow, in Dutch). If contacting the patient by telephone is necessary, the medical assistant will use a call script to assess patients' pain, nausea and physical status (APPENDIX III, call script, in Dutch). The medical assistant will often give appropriate feedback or advice via message or telephone. In case of a possible medical alert or a necessary medication adjustment, the medical assistant will consult the anaesthetist, trainee nurse specialist or physician assistant responsible for remote postoperative pain care.

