#### ii. Secondary study parameters/endpoints (if applicable)

Quality of recovery measured with the quality of recovery questionnaire-15 (QoR-15) (16, 24) at post discharge day at post discharge day 1, 4 and 7.

Postoperative Pain: Experienced postoperative pain (POP) measured with (in-app) NRS for Pain (25) (combined with 11 faces scale) measured at day 1, 4 and 7 post discharge.

Post discharge nausea and vomiting: Experienced post discharge nausea and vomiting (PDNV) measured with the Myles' PDNV assessment scale (21) between intervention and non-intervention group. Measured at day 1, 4 and 7 post discharge.

Medication Dosage and Use: the total dosage of administered analgesics will be assessed during hospital stay and recorded in the medical record. The total dosage of administered analgesics at home after discharge will be assessed by asking patients to indicate which pain medication they have been using. Measured at day 1, 4 and 7 post discharge.

The number of contacts with the hospital, general practitioner or emergency department. All types of contacts (e.g. physically, e-mail, telephone) will be assessed by reviewing the PDMS for registered contacts and by asking the patients to indicate the number of contacts.

Measured at day 1, 4 and 7 post discharge.

The number of surgical complications assessed according to the Clavien Dindo classification of surgical complications (26, 27) will be assessed by reviewing the PDMS and by asking the patients to indicate the number of complications. Measured at day 1, 4 and 7 post discharge.

The number of readmissions. A readmission is defined as an admission to hospital or emergency department for medical care or observation regarding their surgical intervention. Readmissions will be assessed by reviewing the PDMS and by asking the patient to indicate the number of readmissions. Measured at day 1, 4 and 7 post discharge.

Satisfaction: Patients' satisfaction with the provided care will be assessed using a 1-item self-created VAS scale ('not at all to very much', 0-10 range). Satisfaction will be measured at day 1, 4 and 7 post discharge.

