### b. Secondary study parameter(s)

Postoperative pain on post discharge day 1, 4 and 7: Mean, Standard Deviation, Mixed effects linear regression models will be conducted to investigate the effect of the smartphone app on postoperative pain over the first week post discharge as a function of the randomization assignment (i.e. intervention vs control), time (i.e. measurements before surgery, and at day 1, 4 and 7 post discharge), and their interaction term. Random effects, i.e. random intercept, will be fitted per individual to account for clustering effects

Post discharge Nausea and Vomiting (PDNV) on post discharge day 1, 4 and 7: Mean, Standard Deviation and Mixed effects linear regression models will be conducted to investigate the effect of the smartphone app on PDNV over the first week post discharge as a function of the randomization assignment (i.e. intervention vs control), time (i.e. measurements before surgery, and at day 1, 4 and 7 post discharge), and their interaction

term. Random effects, i.e. random intercept, will be fitted per individual to account for clustering effects

Medication Dosage and usage measured in morphine equivalents on post discharge day 1, 4 and 7: Mean, Standard Deviation and Mixed effects linear regression models will be conducted to investigate the effect of the smartphone app on medication dosage and usage over the first week post discharge as a function of the randomization assignment (i.e. intervention vs control), time (i.e. measurements before surgery, and at day 1, 4 and 7 post discharge), and their interaction term. Random effects, i.e. random intercept, will be fitted per individual to account for clustering effects

Difference in the number contacts with the hospital, general practitioner or emergency department (on day 7 post discharge): Mean and Standard Deviation and two sample-t-test (in case of non-normally distributed data we will report on medians and interquartile ranges and differences will be tested using the Mann-Whitney U test)

Difference in the number of surgical complications assessed according to the Clavien Dindo classification of surgical complications (on day 7 post discharge): Mean, Standard Deviation and two sample-t-test (in case of not normally distributed data we will use the Mann-Whitney U test)

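### The complications comparison tests only a plain count and ignores the Clavien Dindo grade, while the app arm alone has clinical contacts that can bring extra events to light

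*Combined protocol and SAP*

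**What the plan says.** The secondary objective (Section 2.c) is a difference between arms in the "number of surgical complications rated with the Clavien Dindo classification". Section 7.a.ii gives the method of ascertainment, which is the same for everyone on days 1, 4 and 7: the complications "will be assessed by reviewing the PDMS and by asking the patients to indicate the number of complications". It does not say how the two sources are combined.

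Section 9.b lists the analysis as "Difference in the number of surgical complications assessed according to the Clavien Dindo classification of surgical complications (on day 7 post discharge", followed by mean, standard deviation and a two-sample t-test, or Mann-Whitney if the data are not normal. It specifies no table or test by grade.

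Clinical contact after discharge differs by arm. In the app arm, "Once a day patients receive a push notification to record pain and nausea" (Section 4.a). After an alert or a question, "an anaesthesia medical assistant will contact these patients during office hours from 08:00 to 16:30 by using the applications' messaging service or by telephone", and if a call is needed, "the medical assistant will use a call script to assess patients' pain, nausea and physical status". For the other arm the Summary states: "The control group receives standard of care (with post-discharge verbal and paper instructions". Among the possible benefits for app patients, the Summary says that "severe pain, nausea and possibly other complications can be noticed and managed earlier".

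**The concern.** An observed number of complications is the product of how many occur and how many are found. In this trial the intervention is itself a form of surveillance. An app-arm patient who triggers an alert or sends a message speaks to clinical staff, who may ask about physical status and may write down what they learn. A control patient with the same minor problem may never contact the hospital. Section 1 itself describes making contact as difficult for a patient who is in pain or worried.

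Grade is what would help a reader interpret a difference. Events serious enough to need hospital treatment are likely to come to light in either arm, whereas minor ones depend more on who is asked and when. That is a judgement and not a figure from the documents. A count that gives every event the same weight cannot separate additional minor findings from real harm. Nor can it show fewer severe events offset by more minor ones, a pattern that earlier management could produce. The trial is non-blinded (Section 3) and no blinded grading of events is described, so nothing else in the plan separates these explanations.

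**Working it through.** **The plan's own figure.** The only sample size is for the primary endpoint (section on sample size calculation): difference 8.0, SD 19.1, two-sided alpha 0.05, power 80%. The normal approximation is 2 × (1.96 + 0.84)² × 19.1² / 8.0² = 89.4, so 90 per group. The exact t-test needs 90.45, so 91, with power 0.802 at 91. With 20% loss, 182 / 0.80 = 227.5, so 228 against the stated 230. The figure reproduces and is not in question. It supplies the arm size used below: 230 / 2 = 115. No rate, effect or power is stated for complications.

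**What is the same and what differs**
- Same in both arms: PDMS review and patient report on days 1, 4 and 7 (Section 7.a.ii), and telephone calls to questionnaire non-responders (Section 7.c).
- App arm only: alerts, in-app messages, triage, and calls where needed (Section 4.a).
- So any extra detection must come through those contacts and what they leave in the PDMS.

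**Effect of unequal detection.** The inputs are assumptions, because the documents give none. Let λ be the true number of complications per patient, equal in both arms, and let d be the share detected. The expected observed number per patient is λ × d, so the observed ratio is d(app) / d(control) whatever λ is:
- 0.8 / 0.7 = 1.14
- 0.9 / 0.7 = 1.29
- 0.9 / 0.5 = 1.80

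Example with λ = 0.2: controls 115 × 0.2 × 0.7 = 16.1 events, app arm 115 × 0.2 × 0.9 = 20.7 events. In simulation the app arm shows the higher count in 75% of trials, against 46% under equal detection (ties make up the shortfall from one half).

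Chance of a significant t-test result (two-sided 0.05) pointing to harm, with no true difference, from Poisson counts at 115 per arm and 10,000 runs:

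| True rate per patient | 0.7 v 0.7 | 0.7 v 0.8 | 0.7 v 0.9 | 0.5 v 0.9 |
|---|---|---|---|---|
| 0.1 | 2.2% | 4.0% | 7.5% | 20.1% |
| 0.2 | 2.5% | 5.7% | 11.1% | 37.3% |
| 0.3 | 2.5% | 6.5% | 14.8% | 50.5% |

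The detection pairs are control v app. Mann-Whitney behaves much the same (10.5% at rate 0.2 with 0.7 v 0.9). At 91 per arm the 11.1% becomes 9.1%.

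**The opposite error.** If the app truly cut complications by 25%, detection of 0.7 v 0.9 would give an observed ratio of 0.75 × 0.9 / 0.7 = 0.96. A real benefit would be almost invisible in the plain count.

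**The case against.** The strongest reply is that the trial's own ascertainment is symmetric. Both arms have the same record review, the same questions on the same days and the same calls to non-responders. The daily prompt asks about pain and nausea, not complications. App contact may be by message, and the call script is used only if a telephone call is needed. The Summary speaks of complications possibly being noticed earlier, and earlier is not more: an event noticed on day 2 instead of day 4 adds nothing to a day-7 count if the patient reports it either way. All of this stands. It narrows the asymmetry to events that surface only through app contact or through record entries that follow from it.

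A reader might also infer more than the documents support:
- That the comparison is biased toward harm in the app arm. Earlier management could also lower the true number, so the net direction is unknown.
- That controls are not followed up. They are, for endpoint collection; what they lack is the additional clinical contact.
- That Clavien Dindo grading is abandoned. The objective, the endpoint and the analysis heading all name it. What is missing is any use of the grade in the comparison.
- That events will be counted twice. The plan gives no rule for combining sources, but Section 9.c requires discrepant data to be resolved before lock, and Section 11.b refers to a data management plan that is not available here. Nothing shows that double counting would differ by arm.

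Finally, the objective is worded as a difference in number, so Section 9.b does analyse what was promised, and the endpoint is secondary and unpowered. If capture were nearly equal (0.80 v 0.85), the ratio would be only 0.85 / 0.80 = 1.06. These points limit the weight of the issue. They do not make an ungraded count interpretable.

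**Conclusion.** The point holds in a limited form. The plan grades complications but compares only their number, in a trial where one arm has additional clinical contact. The comparison can therefore reflect unequal detection, and it cannot reveal a shift between severe and minor events. Under the assumed detection values the spurious ratio runs from 1.14 to 1.80. The chance of a false significant harm runs from 4.0% to 50.5%, against about 2.5% with equal detection. The upper end needs a detection gap of 0.5 v 0.9, for which the documents give no evidence. The figures show sensitivity to assumptions; they do not estimate a bias present in this trial. That the extra events would be mostly minor is likewise a reasonable expectation and not a documented fact. The consequence is confined to one secondary endpoint. The primary QoR-15 analysis and its sample size are unaffected.

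**What to change.** **Section 9.b:** in place of the mean number, compare the arms on the number of patients with any complication and on patients by highest Clavien Dindo grade, descriptively where cells are sparse. Add a sensitivity analysis that excludes events known only through app contact. Because that exclusion can only lower the app-arm figure, read it beside the main result and not as a replacement for it.

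**Section 7.a.ii:**
- Count each event once across the two sources.
- Grade patient-reported events from the patient's description or any available record, without requiring a PDMS entry. Requiring one could remove events of control patients who saw only a general practitioner, and so widen the difference between arms.
- Record every source through which each event was known: app contact, questionnaire, PDMS, other. Recording only the first source would not identify app-only events. A PDMS entry that merely documents an app contact should be coded as app contact.

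**Cost:** two eCRF fields (grade and sources) and a few lines of analysis text. The researchers already review the PDMS. Sources should be captured as data come in, since they are hard to reconstruct later. The drawback is that few events will fall in the higher grades, so that part will be descriptive.

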### **iii. Other study parameters (if applicable)**

The following patient baseline characteristics are collected: age, sex, smoking status, body mass index, ASA classification, PONV score, preoperative NRS, PONV prophylaxis, previous surgical or anaesthesia related complications, history of (chronic) pain, history of motion sickness, surgical specialism, surgical procedure and classification (e.g. laparoscopic cholecystectomy, minor), anaesthesiology technique (i.e. general or spinal anaesthesia), surgery duration, intraoperative medication, PONV and NRS for pain at recovery ward, PONV and NRS for pain at day care ward, duration of admission

### **b. Randomisation, blinding and treatment allocation**

Patients will be allocated to the intervention (remote monitoring) or standard of care group (no remote monitoring). To adjust for practice variation between the participating hospitals Eligible patients will be randomly assigned to receive remote monitoring with the application or the standard of care without remote monitoring. Treatment assignments were performed

centrally according to a computer-generated random schedule (Castor EDC) in permuted blocks of four within strata of participating hospitals (OLVG Hospital, Maasstad Hospital and Canisius Wilhelmina Hospital). The allocation will be computer-generated with Castor© web application (<http://castoredc.com/> and <https://castorcrf.com>, Castor Services are operated by Ciwit B.V. and located in the Netherlands).

### **c. Study procedures**

Patients are recruited to participate in this study during their appointment for anaesthesia pre-assessment (e.g. online assessment, telephone assessment or during visiting the anaesthesia outpatient department). An anaesthesiologist, trainee nurse specialist, physician assistant or medical assistant will verbally explain the study. If interested, they receive an information-letter about the study, and an informed consent form (PIF\_IC\_e1\_e2\_QuReMo\_Versie1\_14\_7\_2021).

Patients who are not informed during the preoperative assessment will be contacted afterwards by one of the researchers to explain the study and to ask them to consider participation. If interested, they receive an information-letter about the study, and an informed consent form (PIF\_IC\_e1\_e2\_QuReMo\_Versie1\_14\_7\_2021).

The patients are given a reflection period of at least 48 hours, after that a researcher or medical assistant will contact the patient if they agree to participate. Patients who have been asked to participate are earmarked in the PDMS (e.g. EPIC). A patient who wishes to participate is asked to sign the consent form and bring it on the day of admission. Patients who, forget to bring their consent form are provided a copy, which is then to be signed on the day of admission. Accordingly, both researchers and patients receive a wet ink copy of the consent form.

After receiving informed consent, the researchers will record the baseline characteristics to the Castor EDC database and perform the randomisation procedure. Moreover, no data is recorded that could trace back the identity of the patients. By randomizing, an anonymous study identification number is allocated to the patients. The researchers from the participating hospitals will keep a secured database in which patient hospital number corresponds with the study identification number, stored locally at their own hospital server. Two days before admission patients in the remote monitoring group (intervention group) receive an invitation e-mail from Luscii © sent by a medical assistant from the anaesthesia outpatient department with instructions to download and install the remote monitoring application. Perioperative patients from both the intervention group and the standard of care group receive anaesthesia

care according to the standards of the Dutch association of anaesthesiologist (18, 19). Intra- and postoperative characteristics and variables will be recorded in Castor EDC by the researchers. Before discharge, patients from both groups receive verbal and paper care and recovery instructions from a day ward nurse. In addition patients receive a medication box with instructions for use, containing paracetamol, naproxen or diclofenac and in case of an intermediate surgical risk for complications also tramadol or an opioid. Once at home, patients in the intervention group can start using the smartphone application for recording pain and nausea and ask additional questions about their recovery. Subsequently an anaesthesia medical assistant will respond appropriately to patients in need following triage and assessment protocol. At day 1, 4 and 7 post discharge patients from both groups receive an online questionnaire (QoR-15). In case patients do not respond, a researcher or a medical assistant will contact the patients from both study arms by telephone to assess the study endpoint questionnaire (f1\_vragenlijst\_QuReMo\_English\_version\_1\_16\_7\_2021 ). Thereafter, endpoint data will be recorded in Castor EDC by one of the researchers.

In addition, patients from the remote monitoring group who have given permission for an interview to assess the quality of communication with app receive a telephone appointment at day 7 postoperative for a 30 minutes semi structured interview with one of the researchers.

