General evaluations regarding provided care after discharge: Patients' evaluations of their experienced care during the 7 day discharge period are measured using two items. i) How likely is it that the patient would recommend this hospital to other day care surgery patients (using an adapted item from the CQ index (0-10 'would definitely not recommend' to 'would definitely recommend') (28, 29). ii) Their overall rating of the quality of care provided by the hospital during the 7 day discharge period, using an item from the CQ index (0-10 scale, 'very poor care' to extremely good care') (28, 29). Both items will be measured at discharge day 1, 4 and 7.

The quality, experiences and communication regarding remote monitoring with this application will be assessed in one by one semi structured interviews. The perceptions of 20 participants are considered satisfactory or when data saturation is reached (REF). Prior to the interview, participants receive general information concerning the topics and informed consent was requested from the interviewee to allow for audio recording of the interview. See for interview topics (f1\_Interview Topics\_version\_1\_11\_2021-). Furthermore, interviews are conducted by telephone or online through Skype, Zoom or FaceTime due to COVID-19 measures.

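### The telephone fallback lets the role that delivers app monitoring also collect the day-7 QoR-15, so an interviewer effect of unknown size can arise in the app arm only

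*Combined protocol and SAP*

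**What the plan says.** **Collecting the endpoint.** Section 7c sends both arms an online questionnaire at days 1, 4 and 7 after discharge. For patients who do not return it, "In case patients do not respond, a researcher or a medical assistant will contact the patients from both study arms by telephone", and the stated purpose of the call is to complete the endpoint questionnaire. Section 7a.i makes the day-7 QoR-15 the primary endpoint. Section 7a.ii schedules satisfaction, likelihood of recommending the hospital and a care rating on the same days. The rating is described as "Their overall rating of the quality of care provided by the hospital during the 7 day discharge period".

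**Delivering the intervention.** Section 4a states that, for app patients who raise an alert or ask for help, "an anaesthesia medical assistant will contact these patients during office hours from 08:00 to 16:30 by using the applications' messaging service or by telephone". Section 7c repeats this: "Subsequently an anaesthesia medical assistant will respond appropriately to patients in need following triage and assessment protocol". The app invitation, which goes to the intervention arm only, is "sent by a medical assistant from the anaesthesia outpatient department with instructions to download and install the remote monitoring application".

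**Safeguards.** Section 3 describes the trial as non-blinded. Section 7b has blinding in its title but describes no blinded assessor. The call script in Section 4a is for triage, and no script is described for the endpoint call. Section 9a plans a sensitivity analysis only if the mixed model suggests bias, and does not say what it would contain.

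**The concern.** The primary outcome is a self-reported score in an open trial, so who asks the questions is one of the few protections left. Section 7c allows the asker to come from the role that looked after the app-arm patient during that same week. People tend to answer more favourably to someone who has helped them, and this applies with more force when the question is about the care itself. Such a shift would raise app-arm scores and would look like the benefit that Section 1 hypothesises, namely that being monitored and receiving feedback improves experienced recovery. It is systematic, so a larger sample does not dilute it. A mixed model without mode or caller in it would not reveal it.

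**Working it through.** **1. The plan's own figure.** Section 3d uses a difference of 8.0, SD 19.1, two-sided alpha 0.05 and a t-test. Power by the noncentral t is 79.8% at 90 per group and 80.2% at 91, so 91 per group is reproduced. With 20% dropout, 182 / 0.8 = 227.5, or 228; the plan's 230 agrees. The sample size is not in question.

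**2. Who does what.**

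| Task | Arm | Role named | Section |
|---|---|---|---|
| Send the app invitation | App | Medical assistant, anaesthesia outpatient department | 7c |
| Triage, message, phone, advise | App | Anaesthesia medical assistant | 4a, 7c |
| Take the endpoint questionnaire by telephone | Both | Researcher or medical assistant | 7c |

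The roles overlap in the app arm, and no sentence keeps the tasks apart.

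**3. What cancels and what does not.** Let p_A and p_C be the telephone shares in the app and control arms, and m the general telephone-versus-online shift. Let f be the share of app-arm scores taken by a medical assistant from a patient whom that role monitored, and b the extra points given to such a caller. Then

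spurious difference = m × (p_A − p_C) + f × b.

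The first term vanishes if non-response is equal in the arms. The second has no counterpart among controls, who receive no monitoring.

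**4. Size.** The documents give neither f nor b, so both are assumed. With SE = 19.1 × √(2/91) = 2.83 and shift s = f × b, the rejection rate when there is no true effect is

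1 − Φ(1.96 − s/SE) + Φ(−1.96 − s/SE).

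| f | b (points) | s = f × b | s / 8 | Two-sided error, 91 per arm |
|---|---|---|---|---|
| 10% | 4 | 0.4 | 5% | 5.2% |
| 20% | 4 | 0.8 | 10% | 5.9% |
| 30% | 4 | 1.2 | 15% | 7.1% |
| 20% | 8 | 1.6 | 20% | 8.7% |
| 40% | 8 | 3.2 | 40% | 20.4% |

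For the 0.8-point case, s/SE = 0.8 / 2.83 = 0.283, which gives 0.047 + 0.012 = 0.059. For the 3.2-point case, s/SE = 1.130, which gives 0.203 + 0.001 = 0.204. With 115 per arm (230 / 2) the same 0.8 points gives about 6.2%: the standard error falls and the bias does not.

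**5. Reading f correctly.** f is not the telephone share. Calls made by researchers, and app patients who never triggered any contact, reduce it. If 20% of app-arm scores came by telephone and researchers took half of them, f would be at most 10%, which is the first row at b = 4. The last row is an upper case: every one of 40% of app-arm scores would have to move by the trial's whole relevant difference.

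**The case against.** The strongest reply is that this is a fallback route, applied by the same roles to both arms, and that a researcher may make any of the calls. A general telephone effect cancels if non-response is similar. Section 9d expects little or no loss to follow-up. All of this limits the size, but it does not remove the app-arm term in step 3. Section 9d concerns outcomes still missing at the end, not the share of online forms that need a call.

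Several stronger readings are tempting, and the documents do not support them:

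- *The same person monitors and scores.* The overlap shown is of role only. Section 7c names a medical assistant for the endpoint call and an anaesthesia medical assistant for monitoring. The same individual is possible but is not stated.
- *Control patients have no relationship with the caller.* Under Sections 4a and 7c, medical assistants may introduce the study and follow up on participation with any patient. Controls may know them too. The difference lies in contact after discharge, and even in the app arm that depends on an alert or a question.
- *The bias could never be detected because mode and date are not kept.* The documents do not list the eCRF fields, and Section 11b refers to a data management plan in an appendix that is not available here. All one can say is that the protocol does not state that these items are recorded.
- *The call itself gives controls something close to the intervention.* Its stated purpose is the questionnaire. The intervention is daily recording, alerts, triage and escalation.
- *Controls are called later and so score higher.* Nothing in the documents indicates this.

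It is also fair to say that researchers are not automatically neutral. Under Section 7c they randomise patients, hold the identification key and interview app-arm patients around day 7. Naming a researcher as caller is therefore not enough without further conditions.

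**Conclusion.** The point holds as a gap in the conduct rules. Section 7c expressly permits the role that delivers app-arm monitoring to collect the primary score and the care ratings by telephone, and no provision separates the two tasks. The resulting effect would be confined to the app arm and would most plausibly favour it.

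The textual finding is firm; the size is not known. The illustration runs from 0.4 to 3.2 points, with 0.8 points and about 5.9% error as a moderate case and about 20% error as an upper case. It rests wholly on assumed values of f and b. That the care ratings are part of the telephoned questionnaire is inferred from their shared schedule, since the questionnaire itself is not reproduced in the documents. This is a cheap improvement worth making. It does not show that the trial's result would be wrong.

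**What to change.** In Section 7c, remove the medical assistant as an option for endpoint calls. Require a researcher who has had no monitoring contact with that patient and is not that patient's interviewer. The caller should work from a list that does not show the arm and should read the items verbatim.

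In Castor, record mode (online or telephone), caller role and completion date if these are not already captured, and report all three by arm.

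An analysis restricted to scores completed online may be added as a prespecified sensitivity analysis. It should carry the caveat that it selects patients on a post-randomisation response and can be biased for that reason.

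The cost is protocol wording and at most three eCRF fields, with no change to the sample size. Researchers would take over calls that medical assistants might have made. The number of calls is not known, so the workload should be checked at each hospital. Patients remain unblinded, so expectation bias in the self-reported score is not removed; the change closes only the part that comes from who is asking.
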